9 ASSESSMENT OF SAFETY AND ADVERSE EVENTS

9.1 Adverse Events

Adverse Event: An adverse event is defined as any untoward medical occurrence in a participant after administration of the investigational vaccine and that does not necessarily have a causal relationship with the investigational vaccine. An AE can therefore be any unfavourable and unintended sign (including abnormal laboratory findings), symptoms, physical examinations, or

disease temporally associated with the use of the investigational vaccine, whether or not related to the investigational vaccine. This definition includes exacerbations of pre-existing conditions. Stable pre-existing conditions which do not change in nature or severity during the study are not considered AEs; however, these should be reported as part of the medical history. AE's will be recorded from D1 after study vaccination up to last visit of the participant. An AE does not include:

- Medical or surgical procedures (e.g., surgery, endoscopy, transfusion), but the condition that leads to the procedure is an AE.
- Situations where an untoward medical occurrence has not occurred (e.g., hospitalization for elective surgery, social and / or convenience admissions).
- Overdose of either study drug or concomitant medication without any signs or symptoms

Information to be collected on AEs includes event description, time of onset, clinician's assessment of severity, relationship to study product, and time of resolution/stabilization of the event. AE assessment should be made only by those with the training and authority to make a diagnosis.

Solicited AEs are pre-specific adverse events that are common or known to be associated with vaccination and that are actively monitored as indicators of vaccine reactogenicity. Investigators will not be required to assess causality of solicited adverse events if the onset is during the solicitation periods. Solicited adverse events with onset after the solicitation period will be captured as unsolicited AEs.

For this trial, immediate AEs will be assessed by study staff 30 minutes after each vaccination and solicited AEs will be assessed daily for 7 days after each vaccination by the participants. Participant parent/LAR will be provided a diary to record the presence or absence of solicited AEs, severity of the solicited AE and use of concomitant medication.

In this study only systemic solicited events of fever, diarrhea, vomiting, decreased appetite, irritability, and decreased activity level will be monitored. Local reactions to EPI vaccination should be reported as unsolicited AEs.

Unsolicited AEs are any AEs reported spontaneously by the participant's parent/LAR, observed by the study personnel during study visits or those identified during review of medical records or source documents. Unsolicited AEs are not specified for active monitoring, but spontaneously reported as untoward events occurring in a participant. All such events will be recorded on the 'Adverse event' pages of the eCRF.

SAEs are defined in Section 9.9.

9.2 AE/SAE Reporting Period and Parameter

The safety profile will be evaluated by the proportion of participants experiencing AEs, related or not related, under the following five categories:

- Number and percentage of participants with immediate adverse events within 30 minutes after each vaccination.
- Number and percentage of participants with solicited adverse events (fever, diarrhea, vomiting, decreased appetite, irritability, and decreased activity level) over the 7-day period (Days 1-7) post vaccination.
- Number and percentage of participants with unsolicited adverse events from first vaccination through four weeks after the last vaccination (Unsolicited adverse events are any untoward

medical occurrence in the participant, temporally related to receipt of the study products, whether or not considered related).

• All serious adverse events (SAEs) and Intussusception from first vaccination through four weeks after the last vaccination.

9.3 Severity of Event

Severity of solicited reactions will be graded as follows:

Reaction	Intensity grade	Parameter	
Fever (°C)	0/Normal	Axillary temperature < 37.5°C	
	1/ Mild	Axillary temperature $\geq 37.5 - \leq 38.0^{\circ}$ C	
	2/Moderate	Axillary temperature $> 38.0 - \le 39.0^{\circ}$ C	
	3/ Severe	Axillary temperature > 39.0°C	
Diarrhea	0/Normal	0 - 2 looser than normal stools / day	
	1/ Mild	3 looser than normal stools / day	
	2/Moderate	4 - 5 looser than normal stools / day	
	3/ Severe	\geq 6 looser than normal stools / day	
Vomiting	0/Normal	Normal (no emesis)	
	1/ Mild	1 episode of vomiting / day	
	2/Moderate	2 episodes of vomiting / day	
	3/ Severe	≥ 3 episodes of vomiting / day	
Decreased appetite	0/Normal	Appetite as usual	
	1/ Mild	Eating/breastfeeding less than usual / no effect on normal activity	
	2/Moderate	Eating/breastfeeding less than usual / interferes with normal activity	
	3/ Severe	Not eating/breastfeeding at all	
Irritability	0/Normal	Normal (Behaviour as usual)	
	1/ Mild	Crying more than usual with no effect on normal activity	
	2/Moderate	Crying more than usual that interferes with normal activity	
	3/ Severe	persistent crying and the child could not be comforted and that prevents normal activity	
Decreased activity	0/Normal	Behaviour as usual	
level	1/ Mild	Drowsiness easily tolerated	

2/Moderate	Drowsiness that interferes with normal activity
3/ Severe	Drowsiness that prevents normal activity

The severity of all unsolicited AEs / SAEs occurring during the course of the study will be graded as per the guidance document by Division of AIDS (DAIDS) Table for Grading the Severity of Adult and Pediatric Adverse Events, corrected version 2.1, July 2017, of the US National Institute of Health as attached as Appendix 2 to the protocol. Severity of unsolicited AEs and SAEs not included in the grading system mentioned above will be graded as follows:

Grade 1 / Mild - Mild symptoms causing no or minimal interference with usual social & functional activities with intervention not indicated.

Grade 2 / Moderate - Moderate symptoms causing greater than minimal interference with usual social & functional activities with intervention indicated.

Grade 3 / Severe - Severe symptoms causing inability to perform usual social & functional activities with intervention or hospitalization indicated.

Grade 4 / Potentially Life Threatening - Potentially life-threatening symptoms with intervention indicated to prevent permanent impairment, persistent disability, or death (the Investigator should not grade a reaction as life-threatening if had it occurred in a more severe form then it might have caused death).

Grade 5 / Death- All AEs leading to death are Grade 5 events.

Definitions:

Usual Social & Functional Activities: Activities that are age and culturally appropriate, such as social interactions, play activities, or learning tasks.

Medical Intervention: Use of pharmacologic or biologic agent(s) for treatment of an AE.

An AE that is assessed as severe should not be confused with the term SAE. Severity is a category utilized for rating the intensity of an event; and both AEs and SAEs can be assessed as severe. AEs characterized as intermittent require documentation of onset and duration of each episode.

AEs are graded with the worst severity grade during the illness/symptoms.

9.4 Relationship to Study Vaccines

The clinician's assessment of an AE's relationship to study product is part of the documentation process. The clinician must determine whether there is a reasonable possibility that the investigational product(s) caused or contributed to an AE. It is essential to have the best assessment possible as to whether adverse events are related to investigational products.

- Is there a temporal (time-based) relationship between the event and administration of the investigational product?
- Is there a plausible biological mechanism for the investigational product to cause the AE?
- Is there a possible alternative etiology for the AE such as concurrent illness, concomitant medications?
- Are there previous reports of similar AEs associated with the investigational product or other vaccines in the same class?

For this study, the clinician must classify the causality of the AE according to the categories defined below:

Related: There is a reasonable possibility that the product caused the event. "Reasonable possibility" means that there is evidence to suggest a causal relationship between the study product and the AE.

Not Related: There is not a reasonable possibility that the administration of the study product caused the event.

Assessment of causal relationship should be recorded in the AE and SAE forms.

Any solicited reactogenicity that occurs during the 7-day period post-injection is automatically regarded as related.

9.5 Guidelines for AEs

To improve the quality and precision of acquired AE data, the PI should observe the following guidelines:

- All AEs and SAEs will be recorded in the source document and eCRF for all participants throughout the study participation.
- A solicited symptom reported during the solicitation period as an SAE should be recorded on the PIDC and SAE forms.
- Whenever possible, use recognized medical terms when recording AEs on the AE CRF. Do not use colloquialisms and/or abbreviations.
- If known, record the diagnosis (i.e., disease or syndrome) rather than component signs, symptoms and laboratory values (e.g., record congestive heart failure rather than dyspnea, rales, and cyanosis). However, signs and symptoms that are considered unrelated to an encountered syndrome or disease should be recorded as individual AEs (e.g., if congestive heart failure and severe headache are observed at the same time, each event should be recorded as an individual AE).
- AEs occurring secondary to other events (e.g., sequelae) should be identified by the primary cause. A "primary" AE, if clearly identifiable, generally represents the most accurate clinical term to record. If a primary serious AE (SAE) is recorded, events occurring secondary to the primary event should be described in the narrative description of the case.

Acute Gastroenteritis→ Diarrhea→ Nappy Rash

The primary AE here is acute gastroenteritis.

- Death is an outcome of an event. The event that resulted in the death should be recorded and reported on the SAE CRF.
- For hospitalizations for surgical or diagnostic procedures, the illness leading to the surgical or diagnostic procedure should be recorded as the SAE, not the procedure itself. The procedure should be captured in the case narrative as part of the action taken in response to the illness.
- While no routine safety laboratories will be performed under this protocol, any abnormal laboratory findings (e.g., clinical chemistry, hematology) or other abnormal assessments (e.g., electrocardiogram, vital signs) that the study team may be aware of are not per se reported as AEs. However, abnormal findings that are deemed clinically significant or are associated with signs and / or symptoms must be recorded as AEs if they meet the definition of an AE (and recorded as an SAE if they meet the criteria of being serious) as described previously. Clinically significant abnormal laboratory or other abnormal findings that are detected after study drug administration or that are present at baseline and worsen following the

For example:

administration of study drug are included as AEs (and SAEs if serious). The Investigator should exercise his or her medical judgment in deciding whether an abnormal laboratory finding or other abnormal assessment is clinically significant. Usually, the abnormality should be associated with a clinically evident sign or symptom, or be likely to result in an evident sign or symptom in the near term, to be considered clinically significant.

9.6 Immediate adverse Events

Immediate adverse events will be assessed 30 minutes after vaccination on Day 1 and Day 57. The 30-minute Reactogenicity Assessment may consists of vomiting, anaphylaxis etc.

Appropriate medical treatment must be readily available in case of an anaphylactic reaction following the administration of the study product. Immediate reactions will be assessed by a study physician or appropriately trained medical staff. All reactions that occur during this time will be recorded on the CRF. Any immediate reaction which meets the criteria for an SAE must also be documented on an SAE form.

Emergency medicine will be available at the study clinic in the event there are any adverse reactions or events occurring among participants participating in this research. If anaphylaxis occurs after vaccination, it must be treated in accordance with the applicable guideline issued by MOH of VN. Treatment for mild reactions after vaccination will be per "Guidance on the treatment of post- injection reactions" of the National Expanded Program on Immunization. The applied treatment methods must be recorded and kept in the participant file.

9.7 Solicited Reactions (Expected Reactions)

Specific systemic reactions will be solicited (specifically asked of participant's parent/LAR) while participants are in the study. These specific reactions, i.e. (fever, diarrhea, vomiting, decreased appetite, irritability, and decreased activity level) will be graded by the study team as per the guidance above.

Solicited Systemic Reactogenicity will be collected through study Day 7. If a solicited sign or symptom has started during the 7 days post vaccination and continues beyond the 7 days, it will continue to be reported as a reactogenicity symptom. Any solicited sign or symptom starting after 7 days post vaccination will be recorded as an "unsolicited AE".

9.8 Unsolicited Adverse Events

Unsolicited adverse events are any AEs that occur any time after the study vaccine is given (temporally related to study product), whether or not deemed "related" to the product, and are not solicited. Unsolicited AEs can be observed by study staff while the participant is at a clinic for a study visit or reported by the participant's parent/LAR at any time. Unsolicited adverse events will be recorded with onset from the time of vaccination up to 28 days after each vaccination. Any solicited sign or symptom starting after 7 days post vaccination will be recorded as an "unsolicited AE".

9.9 Serious Adverse Events

A SAE is any untoward medical occurrence that:

- Results in death,
- Is life threatening,

- Requires inpatient hospitalization* or prolongation of existing hospitalization*,
- Results in persistent or significant disability** / incapacity,
- Is a congenital anomaly or a birth defect,
- Medically important event[#]

NOTE: Investigator-confirmed cases of intussusception will qualify as SAE in the study and will be reported on the SAE form. The term "life-threatening" in the definition of "serious" refers to an event in which the patient was at risk of death at the time of the event; it does not refer to an event which hypothetically might have caused death if it were more severe.

[#]Medical and scientific judgment should be exercised in deciding whether expedited reporting is appropriate in other situations, such as important medical events that may not be immediately lifethreatening or result in death or hospitalization but may jeopardize the patient or may require intervention to prevent one of the other outcomes listed in the definition above. These should also usually be considered serious. Examples of such events are intensive treatment in an emergency room or at home for allergic bronchospasm; blood dyscrasias or convulsions that do not result in hospitalization; or development of drug dependency or drug abuse.

*Hospitalization is an official admission to a hospital. Hospitalization or prolongation of a hospitalization constitutes a criterion for an AE to be serious; however, it is not in itself considered an SAE. In absence of an AE, a hospitalization or prolongation of a hospitalization should not be reported as an SAE by the Investigator through a SAE form, examples of such situations include:

- A hospitalization or prolongation of hospitalization is needed for a procedure required by the protocol.
- Hospitalization or prolongation of hospitalization is part of a routine procedure followed by the center (e.g., stent removal after surgery). This should be recorded in the study file.
- A hospitalization for a pre-existing condition that has not worsened.
- Hospitalization for social reasons.

**Disability is defined as a substantial disruption in a person's ability to conduct normal life functions.

All SAEs reported from the time of first vaccination upto 4 weeks after last vaccination will be reported in the study. All SAEs must be reviewed and evaluated by a study clinician (SAE relationship to study vaccine must be evaluated as outlined in Section 9.4) and recorded on an SAE form and reported, as specified in Section 9.1010. All such SAEs should also be followed until satisfactory resolution or until the investigator deems the event to be chronic or the patient to be stable.

9.10 Reporting Procedures

Serious Adverse Events

All SAEs must be documented and reported to POLYVAC or its designate, even if the investigator considers that the SAE is not related to treatment. The study clinician will complete a **Serious Adverse Event Form** within the following timelines of such events:

- All SAEs, whether related or unrelated, will be recorded on the Serious Adverse Event Form and notified to local IRB and sponsor by fax or email within 24 hours of site awareness.
- All deaths and immediately life-threatening events, whether related or unrelated, will be recorded on the Serious Adverse Event Form and reported to the MOH by fax or email within 7 days of site awareness.

• SAEs other than death and immediately life-threatening events (i.e., events resulting in hospitalization or prolongation of hospitalization, persistent or significant disability or incapacity, or other significant events determined by the investigator to be SAEs), regardless of relationship, will be reported reported to the MOH via fax or email by the site within 15 days of becoming aware of the event.

POLYVAC will be primarily responsible for medical monitoring of serious adverse events documented by the investigator. Medical Officers from PATH serving as technical consultants will review all serious adverse events and provide guidance regarding SAE management, including classification and reporting. Details for review and reporting of serious adverse events and other unanticipated problems will be in an SOP drafted prior to study initiation.

Reporting of AEs

Collected SAEs will be reported to responsible ethical review committees according to their requested timelines. An SOP for reporting to the responsible committees will be developed with reporting requirements and timelines prior to study initiation. It will be the investigator's responsibility to assure that all reportable events are reported to the proper authority, or to POLYVAC, and/or its designate in a timely manner and according to existing SOP. PATH technical consultants may assist the investigator with regulatory reporting, per the finalized SOP.

Other Unexpected Issues/Unanticipated Problems

During study process, if there are any problems related to the trial (unanticipated problems), the Principal Investigator is responsible for reporting to POLYVAC and PATH to discuss reasonable ways of handling the problem. The Principal Investigator is responsible for reporting any unanticipated problems that affect the health, welfare, or rights of study participants, or that may impact the integrity of the study data to the ethics committees involved in the review of the research. The Principal Investigator should maintain written documentation of all unanticipated problems, their reporting, and resolution.

9.11 Duration of Follow Up for AE Resolution

Participants will be monitored throughout the study period for adverse events. AEs come to the attention of site clinicians through interim medical histories, physical examinations and laboratory testing conducted to investigate other illnesses or routine tests. The possible occurrence of any AE and SAE will also be asked during the scheduled study visits. In addition, the parents will be advised to contact study staff immediately at any time throughout the study period if their child experiences an AE. All adverse events will be closely monitored in the safety monitoring processes.

AEs will be managed in accordance with good medical practices by the clinical study site team who will assess and treat or refer the participant for medical care as appropriate. Where feasible and medically appropriate, the parent will be encouraged to seek medical care at the facility where the study clinician is based, and to request that the clinician be contacted upon their arrival. If needed to monitor or treat an adverse event, additional study visits may be conducted.

All AEs and SAEs will be followed until resolution, until the condition stabilizes, or until the participant's participation in the study ends, whichever is earlier. Once resolved or stabilized, the appropriate AE / SAE form(s) will be updated. Participants who have an ongoing study product-related AE/SAE at study completion or at discontinuation from the study will be followed by the PI or his designee until the event is resolved or determined to be irreversible, chronic, or stable by the PI. The Investigator will ensure that follow-up includes any supplemental investigations as

Confidential

may be indicated to elucidate the nature and / or causality of the AE or SAE. This may include additional laboratory tests or investigations, histopathological examinations or consultation with other health care professionals.

POLYVAC or its designee may request that the Investigator perform or arrange for the conduct of supplemental laboratory analysis and / or evaluations to elucidate as fully as possible the nature and /or causality of the AE or SAE. The Investigator is obliged to comply with this request if justifiable. Site Investigators will make sure that the required diagnostic tools (e.g., ultrasound) and surgical treatment for intussusception are readily available for the study participants under his watch. If a participant dies during the study period or during a recognized follow-up period, attempts should be made to provide a copy of any post-mortem findings, including histopathology. The updated SAE form should be sent to the SRC within the time frames outlined in the SOP.

The outcome of adverse event will be assessed as at the time of last observation as per the following categories:

- Recovered/resolved without sequelae
- Recovered/resolved with sequelae
- Ongoing at the end of the study
- Stabilized
- Death
- Unknown. The outcome of the AE is not known

9.12 Safety Oversight

For this study, a diligent mechanism for review of safety of the participants will be planned. It will ensure safety oversight by the site PI and Safety Review Committee (SRC) with provisions for referring to infectious disease specialists in case a consultation is recommended by the SRC.

Routine Reviews by Principal Investigator

The study site Investigators will be responsible for continuous close safety monitoring of all study participants, and for alerting the protocol team if concerns arise or if criteria for expedited review of safety data are met.

Routine Reviews by Safety Review Committee (SRC)

An team of vaccine experts, the SRC, will be established to examine safety at periodic intervals. The SRC, a group of physicians which include but not limit to the designated investigator from study team and the Medical Officer(s) from POLYVAC and PATH, a Pharmacovigilance/Medical officer from the CRO and an independent vaccine expert will routinely monitor safety throughout the duration of the trial. The SRC will be chaired by PATH Medical Officer and may seek additional independent expert medical opinion as dictated by needs. The CRO statistician with assistance from the data management staff will prepare safety reports for review by the SRC. These reports will provide at a minimum the following information: 1) accrual and participant status data with regard to completion of study vaccinations and study visits; and 2) summaries of solicited and unsolicited adverse events during the review period 3) Reported SAEs.

The SRC safety review will be conducted by email/teleconference occurring approximately fortnightly to monthly (depending on rate of enrollment) during the vaccination phase of the study and as needed thereafter for the remainder of the study. An expedited safety review will be carried out within 36 hours of submission of the safety information for the safety events listed below:

Event and relationship to study agent*	Severity Grade
SAE, related	All grades
A case of Intussusception	All grades
Unsolicited AE, related	4 and above
* As assessed by investigator or Medical Monitor	

The designated investigator or an assigned medical monitor/officer will be responsible for informing the other members and convening an ad hoc safety review whenever it is aware of an SAE or adverse event that meets any of the criteria above. The SRC may seek independent expert medical opinion as dictated by the occurrence of certain events.

In addition to safety review, the SRC may elect to discuss trial conduct issues that impact study integrity and participant safety. These may include but not limited to data quality, critical monitoring findings, study product, research specimens, etc.

The reports and their analysis by the SRC will be submitted to the various ECs/IRBs, if needed. The Terms of Reference for the SRC will be developed.

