5.2.2 Blinding and Unblinding Procedures

The study will be conducted according to a partially blinded study design since the colour of the two vaccines is different. With the exception of the designated unblinded site personnel described below, all study site personnel, the PI, PATH, POLYVAC and the CROs, will remain blinded to subjects' treatment assignments until first database closure and study unblinding. The randomization list for participants will be developed by an independent statistician and will be used by an unblinded team at POLYVAC to label study vaccine vials and then it will be immediately sealed. During conduct of the study, a limited number of unblinded site personnel will be responsible for preparing and administering study vaccines, performing vaccine accountability, and maintaining the security of the treatment assignments. The unblinded site personnel will not be involved in the safety assessment of the subjects or in any other aspect of the study. All other site personnel, including those who perform the clinical evaluations (such as but not limited to assessment of medical history, vital signs assessment, and PE), will be blinded with respect to the identity of the vaccine administered to the subjects.. The parents will also remain blinded to the treatment received by the child, throughout the study duration. To maximize blinding the two formulations of ROTAVIN vaccine vials will be packaged and labeled in such a way that they have similar appearance. Also, in addition to the original vial label of the vaccines designed by POLYVAC in compliance with the drug labeling regulations of the Ministry of Health, an identical study label designed for study vaccines containing only the study product code will be pasted over the original vial label to ensure implementation of blinding. The labeling will be done by an unblinded team at POLYVAC before study vaccines are shipped to the study site.

Study product administered to each participant will be recorded using the exact allocation code for each product received by each participant. The allocation codes which link treatment identification with each participant via participant identification numbers will be maintained in a secure location and managed by individuals who are not directly implementing or monitoring the trial. The

allocation code listing will not be opened or linked to the clinical trial database until after the database is locked.

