With 550 vaccinated participants in ROTAVIN liquid formulation group and 275 vaccinated participants in ROTAVIN-M1® group, the study has 90% power to detect at least a 6.8% difference in percentage of participants with solicited post-vaccination reaction between the ROTAVIN liquid formulation and ROTAVIN-M1® groups after each vaccination, assuming that the rate of the solicited reactogenicity is 5% in the ROTAVIN-M1® group and a significance level of 0.05. Interim Analyses and DSMB Safety Reviews

There are no planned interim analyses or DSMB safety reviews. The SRC will meet monthly to review the blinded data to discuss any safety concerns.

6. General Statistical Considerations

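### A death or life-threatening SAE (other than intussusception) that neither the investigator nor the Medical Monitor calls related does not trigger the 36-hour Safety Review Committee review

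*Protocol*

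**What the plan says.** **Expedited review.** Protocol 9.12 sets the rule: "An expedited safety review will be carried out within 36 hours of submission of the safety information for the safety events listed below". The table beneath it has three rows:

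1. an SAE judged related, any grade;
2. "A case of Intussusception", any grade, with no condition on causality;
3. "Unsolicited AE, related", grade 4 and above.

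The footnote on relationship reads "As assessed by investigator or Medical Monitor", so a finding of relatedness by either person is enough.

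**Routine review.** Protocol 9.12 has SRC reviews "occurring approximately fortnightly to monthly (depending on rate of enrollment) during the vaccination phase of the study and as needed thereafter". The SAP, at the end of section 5, says that no interim analysis or DSMB review is planned and adds: "The SRC will meet monthly to review the blinded data to discuss any safety concerns".

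**Reporting.** Protocol 9.10 does not separate the gravest events by causality: "All deaths and immediately life-threatening events, whether related or unrelated, will be recorded on the Serious Adverse Event Form", and they go to the MOH within 7 days. The same section sends every SAE to the local IRB and sponsor within 24 hours and has PATH Medical Officers review all SAEs. Protocol 9.11, in the paragraph that covers a participant's death, sends the updated SAE form to the SRC on a timeline held in an SOP.

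**The concern.** The committee's fast route depends on causality for every event except intussusception. A fatal event is grade 5 under Protocol 9.3, but grade alone opens no row, so a death called unrelated is treated for this purpose like any other unrelated SAE.

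One purpose of a safety committee is to test the causality calls made on the gravest events. Here those calls are binary (Protocol 9.4), and site staff, the PI, the sponsor, PATH and the CROs are blinded apart from designated staff: "all study site personnel, the PI, PATH, POLYVAC and the CROs, will remain blinded to subjects' treatment assignments". With no DSMB review planned, the SRC is the only standing safety committee described. Its membership list names one member as independent, the vaccine expert. If a wrong *not related* call is made on a death, the plan sets no short limit for that expert and the full committee to look at it. The participants are healthy infants receiving a live vaccine in a new formulation.

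**Working it through.** This is a check of rules against rules, with a small calculation of waiting time. The plan's only figure here, 36 hours, is a procedural limit and not a calculated quantity, so there is nothing to reproduce.

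**Step 1: put the event through the table.** Take a death or immediately life-threatening SAE that is not intussusception and that neither assessor calls related.

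| Row in Protocol 9.12 | Met? | Reason |
|---|---|---|
| Related SAE, all grades | No | Not judged related by either assessor |
| Intussusception, all grades | No | Excluded by assumption |
| Related unsolicited AE, grade 4 and above | No | Grade is met, relatedness is not |

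No row is met. If the Medical Monitor alone calls the event related, row 1 is met. A solicited reaction in the 7-day window counts automatically as related under Protocol 9.4, so one that becomes an SAE also appears to meet row 1. The gap lies outside these cases.

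**Step 2: the wait for the next scheduled SRC review.** Inputs are the fortnightly to monthly cycle (Protocol 9.12), a month taken as 30 days (assumption), and the 36-hour limit.

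- Fortnightly, longest wait: 14 × 24 = 336 hours; 336 / 36 = 9.3 times the expedited limit.
- Monthly, longest wait: 30 × 24 = 720 hours; 720 / 36 = 20 times the limit.
- Average wait, if events fall evenly between meetings: 14 / 2 = 7 days to 30 / 2 = 15 days.
- After the vaccination phase: no maximum under the protocol, about 30 days under the SAP's monthly meeting.

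**Step 3: what the other routes guarantee for the same event.**

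| Route | Time limit stated | Brings in the full SRC and its independent expert? |
|---|---|---|
| Sponsor and local IRB notice, all SAEs (9.10) | 24 hours | No |
| MOH notice, deaths and life-threatening events (9.10) | 7 days | No |
| PATH Medical Officer review, all SAEs (9.10) | None | No; a PATH Medical Officer chairs the SRC, but this is not a committee review |
| Updated SAE form to the SRC (9.11) | In an SOP, not given | Delivers a form; no meeting is required by the text |

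The MOH can therefore hold the report (7 days) before the next scheduled committee review (up to 14 to 30 days).

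**The case against.** The case for leaving the table alone is substantial.

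- **Intussusception is already covered without a causality filter.** It is the class risk that the protocol singles out. This stands, and it means that a reader who infers that only related SAEs open the fast route has misread the table.
- **No single opinion decides.** Either assessor can trigger review, and PATH Medical Officers review every SAE, including its classification. This stands against any claim that one blinded investigator's view settles the matter.
- **The event is not unseen.** Sponsor and IRB know within 24 hours, and members of the SRC come from bodies that receive or review all SAEs. Investigators must raise concerns whether or not the table is met, and nothing bars an earlier ad hoc meeting. A reader might infer that an unrelated-labelled death simply waits; the documents support that only for scheduled review by the committee.
- **Sections 9.10 and 9.12 do different jobs.** One governs notifying authorities, the other convening a committee, so different thresholds are not a contradiction. This stands. The comparison shows only that the protocol already has a causality-free class that could be reused.
- **Convening a blinded committee adds no allocation information.** Correct. The gain is a prompt collective view of causality that includes the independent expert.
- **The SAE SOP and the SRC Terms of Reference are not available here.** They may contain further triggers. This limits the conclusion to what the protocol and SAP themselves guarantee.
- **Such events should be rare.** The earlier phase III trial of the comparator in 800 infants reported three SAEs, all more than 40 days after vaccination and all with recovery (Protocol 2.5.3). This lowers the expected benefit of a change, and equally its burden.

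What is not answered is the lack of any stated short limit for full-committee review of this class.

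**Conclusion.** The point holds in a narrow form. It concerns deaths and immediately life-threatening SAEs, other than intussusception, that neither assessor judges related. For these the protocol and SAP guarantee no expedited SRC review. The longest wait for a scheduled one in the vaccination phase is about 14 to 30 days (9.3 to 20 times the 36-hour limit), with an average of about 7 to 15 days. It would be wrong to quote 14 to 30 days as the typical delay. After that phase the protocol gives no interval and the SAP gives a month, a difference to be reconciled.

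The conclusion assumes a 30-day month, meetings held on schedule, events falling evenly between them for the average, and no further trigger in the SOP or Terms of Reference. It does not support a claim that serious events go unmonitored, that a stated requirement is breached, or that any endpoint or analysis is affected. It is a cheap improvement to safety oversight.

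**What to change.** Add one row to the trigger table in Protocol 9.12, and carry it into the SRC Terms of Reference, which Protocol 9.12 says are still to be developed: *Death or immediately life-threatening SAE, regardless of relationship; all such events*. Keep the existing three rows. This reuses the class that Protocol 9.10 already defines, so no new event definition is needed.

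State one routine SRC interval in both protocol and SAP, including what applies after the last vaccination, and check that the SOP timeline for sending SAE forms to the SRC fits the 36-hour limit.

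The cost is a small protocol amendment with its approvals, a matching SAP edit, and an occasional extra ad hoc teleconference. Few such events are expected in 825 healthy infants followed for 3 to 4 months. Sample size, endpoints and analyses are unchanged.
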